### **7.1 screening machine**

All subjects were required to complete relevant examinations during the screening period before enrollment, and were screened according to the admission criteria.

- (1) Sign informed consent;
- (2) Record demographic data: date of birth, gender, initials;
- (3) Medical history and physical examination (including vital signs, height, weight, physical examination of the whole body system; Past and present history of HCC,

etiology;

- (4) Other laboratory tests, such as blood routine (white blood cells, neutrophils, hemoglobin, platelets, etc.), urine routine (urine white blood cells, urine protein, red blood cells), stool routine (stool occult blood);
- (5) Liver function (albumin, aminotransferase), kidney function (filtration rate, creatinine), neuron-specific enolase, interleukin 6, etc ;
- (6) Consciousness level assessment: GCS score.

## **7.2 therapeutic session**

### **(1) Treatment plan:**

Test group: Subjects will use conventional rehabilitation therapy (exercise training, physical factor therapy, etc.) and drug therapy (such as controlling blood pressure, blood sugar, promoting microcirculation, nutritional nerve and other supportive treatment) + Tongyuan acupuncture method: point selection: Baihui, Zhongwan, Guanyuan, Qihai, Tianshu (double); Point selection criteria: the national standard "Name and Location of points" (GB/T12346-2006). Intervention time: once a day, 5 days a week for 4 consecutive weeks. Twenty days in total.

Control group: Subjects will receive conventional rehabilitation treatment (exercise training, physical factor therapy, etc.) and drug treatment (such as symptomatic support treatment for controlling blood pressure, blood sugar, promoting microcirculation, nutritional nerve, etc.) + pseudacupoint method (acupuncture treatment is performed 1cm apart from the selected points of the experimental group), once a day, 5 days a week, for 4 consecutive weeks. Twenty days in total.

### **(2) Evaluation:**

Consciousness levels were assessed before intervention, at 1, 2, 3, and 4 weeks of treatment, and 4 weeks after discharge: GCS score, NIHSS score, CRS-R Scale (Modified Coma Recovery Scale), and FOUR scale score . Electroencephalogram, brainstem auditory evoked potentials and encephalofluctuograph were examined before intervention and at 4 weeks of treatment.

## **7.3 follow-up period**

Consciousness level assessment: GCS score, NIHSS score, CRS-R scale, FOUR

scale score.

## **8. evaluation index**

8.1 Evaluation of effectiveness: Before and after the intervention and at 4 weeks of treatment: GCS score.

8.1.1 Glasgow Coma Scale (GCS) : 3 to 15 points

Open eyes (E) : 1-4 points; Vocalization (V) : 1-5 points; Exercise (M) :1-6 points.

The consciousness improvement rate of each patient was calculated according to the following formula:

Consciousness improvement rate of each patient = (score after treatment - score before treatment)/score before treatment  $\times 100\%$

Consciousness improvement rate  $\geq 20\%$  is effective,  $15\% \leq$  consciousness improvement rate  $< 20\%$  is effective, good consciousness

Turnover rate  $< 15\%$  is invalid

Efficiency = (obvious + effective)/(obvious + effective + ineffective)  $\times 100\%$

8.1.2 Revised Coma Recovery Scale (CRS-R) : 0-23 points

The minimum state of consciousness (MCS) was assessed as: visual  $> 1$  or auditory  $> 2$  or verbal response  $> 2$  or motor  $> 2$  or communication  $> 0$  or arousal  $> 2$ ;

The evaluation criteria of persistent vegetative state (VS) were: vision  $\leq 1$  score, hearing  $\leq 2$  score, speech response  $\leq 2$  score, movement  $\leq 2$  score, communication = 0 score and arousal  $\leq 2$  score;

Clarity of mind was assessed on a scale of exercise = 6 points or communication = 2 points.

A change from below MCS to MCS, or from MCS to VS, or from VS to clear consciousness, or an increase of one level or more in the state of consciousness is considered valid.

8.2 Safety evaluation: Events such as needle dizziness, hematoma and unstable vital signs were recorded in the case report and reported to the trial designer. After group discussion, the case was withdrawn from the study. Follow-up of subjects after adverse events: in-hospital monitoring, 1 week after discharge, 4 weeks back to the hospital for re-examination.

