Although some patients have spontaneity or eye opening after stimulation, they lack perception and understanding of internal and external environment and cannot communicate effectively with the outside world, which is called vegetative state (VS) [1]. In recent years, some scholars believe that when patients with vegetative state present fluctuating consciousness, but it is insufficient for reliable communication, it is called minimally conscious state (MCS)[2].

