#### 1.1.3 Assessment of disturbance of consciousness:

The commonly used consciousness assessment methods include behavioral scale assessment, neuroelectrophysiology assessment, neuroimaging assessment and serum marker assessment.

1.1.3.1 Behavioral scale assessment: For patients with consciousness disorders, the most commonly used clinical scales mainly include Glasgow Coma Scale (GCS) and Full Outline of Unresponsiveness scale (Full Outline of Unresponsiveness).FOUR) and revised Coma Recovery Scale-R (CRS-R).GCS

scale is the best choice for consciousness assessment of patients with acute brain injury. CRS-R scale is divided into 6 parts, including auditory (0-4 points), visual (0-5 points), motor (0-6 points), speech (0-3 points), communication (0-2 points) and arousal (0-3 points) assessment, with a total score of 0-23 points, is currently an internationally recognized measurement tool for identifying vegetative state (VS) and minimal state of consciousness (MCS). When patients communication =2 points or movement =6 points, that is, emergence from minimally conscious state (EMCS) [3]. MCS was assessed on the following criteria: visual > 1 or auditory > 2 or verbal response > 2 or motor > 2 or communication > 0 or arousal > 2; The evaluation criteria of VS were: vision  $\leq 1$  score, hearing  $\leq 2$  score, speech response  $\leq 2$  score, movement  $\leq 2$  score, communication = 0 score and arousal  $\leq 2$  score; Clarity of mind was assessed on a scale of exercise = 6 points or communication = 2 points [4-5]. However, it is not sensitive to the identification of MCS patients, and it cannot accurately assess patients with closed eye disorder caused by other reasons such as eye trauma [6]. FOUR patients with locked-in syndrome can be identified by removing speech ability from GCS [7]. The revised Coma Recovery Scale can be used to distinguish subtle differences in the level of consciousness and to monitor the return of consciousness [8]. The scale consists of 6 subscales covering auditory, verbal, visual, communication, motor, and arousal levels, and includes 23 hierarchical grading scales. CRS-R and its operation manual are available in Chinese and have been verified for reliability and validity.

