## **3.study endpoint**

3.1 Primary endpoint: GCS score.

3.2 Secondary endpoints: CRS-R Scale (Coma Recovery Scale-Revised), EEG(electroencephalograph), BAEP (Brainstem Auditory Evoked Potential), and EFG (Encephalofluctuography).

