### **5.2 inclusion criteria:**

(1) sign the informed consent voluntarily;

(2) met the above diagnostic criteria, and the GCS score was between 3 and 9 (the score was scored by a rehabilitation physician, and the patient had not used sedatives or anesthetics on the day of the score);

- (3) The patient's condition is stable, vital signs are stable, and the onset time of consciousness disturbance caused by stroke is confirmed to be less than 6 months;
- (4) Cerebral infarction or cerebral hemorrhage confirmed by clinical and auxiliary examination is the only factor causing consciousness disorder, excluding other diseases caused consciousness disorder patients;
- (5) those aged between 18 and 85;
- (6) Family members or authorized principals know and sign informed consent;
- (7) did not enter other clinical studies at the same time.

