### **13.3 Statistical method**

The analysis included case distribution, demographic data, baseline analysis and therapeutic effect analysis. Baseline data included sex, age, stroke type, stroke duration, underlying medical history (diabetes, hypertension, heart disease, chronic obstructive pulmonary disease), and history of smoking and alcohol use. Baseline data were tested by chi-square test. The end point data was the score of the State of Consciousness scale, and the measurement data was expressed as mean SD. Univariate analysis of variance was used to compare the difference between groups at the same time point, the difference at different time points in the group, and the difference before and after between the two groups.  $P < 0.05$  was considered statistically significant, and multiple comparisons were performed by Dunnett-t test.

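### The CRS-R response rule lists a move from MCS to VS as a success, so any CRS-R response rate built on it would count some patients who got worse as responders

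*Combined protocol and SAP*

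**What the plan says.** Section 3.2 lists the scale among the "Secondary endpoints: CRS-R Scale (Coma Recovery Scale-Revised" and other measures. Section 8.1.2 gives cut-offs on the six subscales for MCS, VS and clear consciousness, and then the response rule. The rule first lists three moves, "A change from below MCS to MCS, or from MCS to VS, or from VS to clear consciousness", and then adds "or an increase of one level or more in the state of consciousness is considered valid".

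The background sets out the order of the states. Section 1.1.1 describes VS as lacking perception and understanding of the surroundings, and then says that "when patients with vegetative state present fluctuating consciousness, but it is insufficient for reliable communication, it is called minimally conscious state (MCS". Section 1.1.3.1 gives the cut-off that 8.1.2 uses for clear consciousness and names it as leaving MCS: "When patients communication =2 points or movement =6 points, that is, emergence from minimally conscious state (EMCS". The order is therefore VS, then MCS, then clear.

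For the analysis, Section 13.3 states that "The end point data was the score of the State of Consciousness scale", summarised by mean and SD and compared by analysis of variance. Neither 13.3 nor 13.4 names a test of a CRS-R response rate.

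**The concern.** The list in 8.1.2 runs below MCS, MCS, VS, clear, which puts VS above MCS. That contradicts the cut-offs just before it and the background. It also contradicts the closing clause of its own sentence, which speaks of a rise in level.

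Taken literally, a patient in MCS at baseline is a success after falling to VS and a failure if stable. If a CRS-R response rate is reported under this rule, falls are added to the successes in both arms. If falls are commoner in the control arm, a true benefit is diluted. If they are commoner with acupuncture, the response rate flatters acupuncture by counting its falls in its favour.

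**Working it through.** The plan states no figure on this point, so the check is of the rule itself.

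**Inputs.** Subscale ranges are from Section 1.1.3.1 and cut-offs from Section 8.1.2.

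| Subscale | Range | MCS if any | VS if all | Scores allowed in VS |
|---|---|---|---|---|
| Auditory | 0–4 | >2 | ≤2 | 3 |
| Visual | 0–5 | >1 | ≤1 | 2 |
| Motor | 0–6 | >2 | ≤2 | 3 |
| Speech | 0–3 | >2 | ≤2 | 3 |
| Communication | 0–2 | >0 | 0 | 1 |
| Arousal | 0–3 | >2 | ≤2 | 3 |

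Clear consciousness is motor = 6 or communication = 2. The maxima sum to 4 + 5 + 6 + 3 + 2 + 3 = 23, which matches the stated range of 0–23.

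**Step 1: which states exist under the cut-offs.**
- All profiles: 5 × 6 × 7 × 4 × 3 × 4 = 10,080.
- VS: 3 × 2 × 3 × 3 × 1 × 3 = 162.
- Meeting MCS: 10,080 − 162 = 9,918. MCS is the exact complement of VS, so no profile meets both and none meets neither.
- Clear: motor = 6 gives 10,080/7 = 1,440; communication = 2 gives 10,080/3 = 3,360; both give 10,080/21 = 480. The total is 1,440 + 3,360 − 480 = 4,320, and all of these also meet MCS.
- MCS but not clear: 9,918 − 4,320 = 5,598.
- Below VS: 0. The all-zero profile is VS, so below MCS and VS are the same set.

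These are counts of possible score patterns, not of patients.

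**Step 2: direction of the disputed move.** MCS needs at least one subscale above its threshold and VS needs none, so every move from MCS to VS lowers at least one subscale. The total need not fall. Of the 5,598 × 162 = 906,876 possible pairs, it falls in 858,817 (94.7%), is unchanged in 23,826 and rises in 24,233. The move is thus always a fall in category, and category is what the rule scores.

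**Step 3: what the rule calls valid.** Clear is treated here as separate from MCS.

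| From \ To | VS | MCS | Clear |
|---|---|---|---|
| VS | no | yes (first item) | yes (third item) |
| MCS | **yes (second item)** | no | yes (closing clause only) |
| Clear | no | no | no |

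Four of nine moves are valid and three are upward. The first and second items together credit crossing the VS/MCS border in either direction.

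**Step 4: possible size.** Let m be the share in MCS at baseline and w the share of those who fall to VS. The rule adds m × w to an arm's response rate, so the bias in the difference (treated minus control) is m × (w_T − w_C). The documents give neither m nor w; all values below are assumed.
- Falls of 5% treated and 15% control: 0.3 × (−0.10) = −3 points; 0.5 × (−0.10) = −5 points, against acupuncture.
- Falls of 15% treated and 5% control: +3 to +5 points, in favour of acupuncture.
- Falls of 10% in both arms: no bias in the difference, but each arm's rate rises by 3–5 points. With the 76 per group of Section 13.1, that is 0.3 × 0.10 × 76 = 2.3 to 0.5 × 0.10 × 76 = 3.8 patients.

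**The case against.** The strongest reply is that no planned analysis uses the rule. Section 3.2 names the scale rather than a responder rate, Section 13 compares scores, and 8.1.2, unlike the GCS rule in 8.1.1, gives no formula for a rate. This stands, and it limits the consequence. But a response definition for a named secondary endpoint invites use, and the plan does not say that it will go unused.

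A second reply is that the labels were probably swapped in drafting and that the closing clause shows the intent. A swap is likely, but the clause is joined by an or, so it adds a route to success and removes none. Undoing the swap gives below VS to VS, VS to MCS and MCS to clear, and the first of these starts from a level that the cut-offs leave empty. Section 1.1.1 does describe coma apart from VS, and entry requires that "the GCS score was between 3 and 9", which reaches the bottom of the GCS, so a fourth level may be meant. The CRS-R cut-offs still do not separate it from VS. If a fourth level is intended, the count of nine moves no longer applies, but MCS to VS remains a fall.

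A third reply is that harm would show elsewhere. This is fair: CRS-R scores, GCS, FOUR and NIHSS are recorded at the same visits. The distortion would be in the CRS-R response rate, not in all the evidence on deterioration.

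**Conclusion.** The concern holds. As written, the rule scores a fall in category as a response, and nothing elsewhere in the documents corrects it. The conclusion rests only on the plan's own cut-offs and on its order of states.

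The consequence is conditional: a CRS-R response rate must be reported, and some patients must fall from MCS to VS. The size cannot be estimated from the documents. The 3–5 points in either direction depend on an assumed 30–50% in MCS at baseline and an assumed 10-point gap in fall rates. The GCS primary endpoint, the sample size and the comparison of CRS-R scores are untouched. The rule should be corrected, but the point does not threaten the main result.

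**What to change.** In Section 8.1.2, delete the move from MCS to VS. Define response only as an upward move of at least one level on an ordered scale with exclusive levels: VS, then MCS not meeting the clear criterion, then clear (motor = 6 or communication = 2). State that any downward move is not a response. The deletion loses no credit for a rise from VS to MCS, because the upward rule covers it.

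The sponsor should state whether a level below VS, such as coma, is intended and, if so, how it is told apart from VS on the recorded scores. The order then gains that level.

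The sponsor should also state whether a CRS-R response rate will be analysed and, if so, at which visit and with which test. Otherwise, the plan should say that the rule is not used.

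The cost is one sentence in 8.1.2 and, if a rate is to be analysed, one line in 13.3. No new data are needed, because the classification uses only the six CRS-R subscales already scored. The change should be made before database lock, so that who counts as a responder is not decided after the data are seen.

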## **9. Safety monitoring, reporting and medical treatment**

### **9.1 Adverse event (AE) definition**

An adverse event is any adverse medical event that occurs after a patient or subject receives a drug that is not necessarily causally related to the treatment. Therefore, an adverse event can be any adverse physical sign (including abnormal laboratory results), symptom, or disease that has a time correlation with the use of the investigational drug, regardless of whether a causal relationship with the investigational drug is considered. Adverse events include Serious adverse events (SAE) and non-serious adverse events.

### **9.2 SAE definition**

SAE refers to the occurrence of medical events during clinical trials that require hospitalization or prolonged hospitalization, disability, affect work ability, endanger life or death, and lead to congenital malformations. Includes the following medical events:

- 1) events leading to death;
- 2) life-threatening events (defined as subjects in immediate danger of death at the time of the event);
- 3) Events requiring hospitalization or prolonged hospitalization;
- 4) Events that can cause permanent or severe disability/disability/affect the ability to work;
- 5) Congenital abnormalities or birth defects;

Other medically important events (defined as events that endanger subjects or require intervention to prevent the occurrence of any of the above).

### **9.3. Adverse event recording, collection, reporting and handling**

#### **9.3.1 Collection, reporting and handling of AE**

From the signing of the informed consent to the beginning of the test, all AE related to the operating procedures specified in the test protocol shall be recorded in the eCRF...

The recording of AE should include: description of the AE and all related symptoms, time of occurrence, severity, duration, correlation with the means of the

test, measures taken, and final results and outcomes. The recording of AE must use medical terminology, and if the subject's signs and symptoms can be summarized by a common cause, the diagnosis should be recorded as far as possible. In addition to indicators related to disease progression, all clinical events and clinically significant laboratory adverse events can be treated with reference to the Common Adverse Event Evaluation Criteria (CTCAE) version 5.0. Adverse reactions to treatment will be recorded by the investigator.

### **9.3.2 SAE collection and reporting**

All SAE, regardless of cause or drug correlation, occurring from the time the subject signed the informed consent to the completion of the trial intervention within 4 weeks were to be reported using the SAE Report Form. In case of SAE, the researcher should immediately take appropriate treatment measures for the subject, ensure the safety of the subject, and report within 24 hours to the applicant for drug registration, the State Drug Administration, the provincial Food and Drug Administration, the ethics committee of the relevant clinical trial center and the medical Department of the Medical Administration Bureau of the Health Commission, and timely report to the ethics committee of the group leader. The first report should, as far as possible, include the following: source of the report, name of the trial intervention, name of the serious adverse event, time of occurrence, severity, duration, association with the trial drug, action taken, and outcome.

### **9.3.3 gestation**

Pregnant patients were not included in this study. Since the included subjects were hospitalized patients with consciousness disorder, the possibility of pregnancy during the study period was excluded.

### **9.3.4 Criteria for judging the severity of AE**

Researchers will evaluate severity according to the five-level criteria developed by the NCI CTCA version 5.0:

Grade 1, mild; Asymptomatic or with mild signs; For clinical or diagnostic observation only, without medical intervention;

Grade 2, moderate; Age-appropriate limited functions of daily living (such as

cooking, shopping, making phone calls, etc.);

Grade 3, serious or medically important but not immediately life-threatening; Resulting in hospitalization or prolonged hospitalization; Disability; Limited daily self-care activities (daily self-care activities refer to bathing, dressing, undressing, eating, toilet use, medication, etc., but not bedridden);

Level 4, life-threatening, requiring emergency treatment;

Level 5, AE-related death

### **9.3.5 Other investigator responsibilities during**

**follow-up of serious adverse events**

Serious adverse events should be examined and treated according to clinical judgment, including necessary clinical laboratory examination and physical examination. The results of any inspection or other updated SAE-related information obtained must be reported in a follow-up report within the same time frame and process as the initial report.

## **10. Trial termination/suspension criteria**

10.1 Sponsor reserves the right to terminate/suspend this trial. Before terminating/suspending a clinical trial, the sponsor must notify the investigator, the Ethics Committee and the State Food and Drug Administration and state the reasons. After the early termination/suspension of the study, the restart of the study must be reviewed and approved by the Ethics Committee;

10.2 Termination/suspension requested by the Ethics Committee.

## **11. Regulations to end clinical trials.**

The trial ends when all subjects meet the following conditions:

- 1) All subjects completed at least 6 months of survival follow-up;
- 2) or the death, loss of follow-up, or withdrawal of informed consent of all subjects.

## **12. data administration**

### **12.1 data administration**

- 1) The researcher must ensure that the data is true, complete and accurate;
- 2) When any correction is made to the test record, the revised data can only be underlined, annotated by the margin, and the reason should be stated. The original

record should not be erased or overwritten.

3) Complete laboratory inspection items.

## **12.2. Data recording and file preservation**

Subject data on the case report form should be recorded in subject code and subject can only be identified by subject code or their initials.

From data entry to the verification requirements of the source data to the question answer of the quality control data, and finally to the operation of data locking and export, after confirming that the data is no doubt, all parties sign the database locking application form, and the data administrator locks the database. After the database is locked, the data administrator exports the analysis database and sends it to statisticians for statistical analysis. The locked data cannot be edited again, and the problems found after the database is locked can be corrected in the statistical analysis program after confirmation.

